5 RATIONALE, OBJECTIVE AND BENEFIT-RISK ASSESSMENT

5.1 Rationale for performing the trial

The proposed phase 2/3 international multi-center trial evaluates the efficacy and safety of intracerebroventricular (intracerebroventricular meaning administration of a medicinal product into the cerebral ventricles (cerebral ventricular system) of the brain) ^{131}I -omburtamab as well as the dosimetry in pediatric NB patients with CNS/LM metastases. The findings of the proposed trial will expand and be compared with the findings of the single center trial of intracerebroventricular ^{131}I -omburtamab in pediatric patients with NB CNS/LM metastases treated in the MSK Trial 03-133. The aggregate findings from the two trials evaluating patients from several centers in the US as well as Europe seek to provide a basis for establishing ^{131}I -omburtamab as the next generation treatment of NB patients with CNS/LM metastases.

5.2 Rationale for dose selection

5.2.1 ^{131}I -omburtamab

[REDACTED]

A second treatment cycle of ^{131}I -omburtamab was administered 5 weeks after the first dose under the condition that the first treatment cycle was tolerable and without objective disease progression. The administered dose was adjusted in children under 3 years of age, as is standard for intracerebroventricularly administered therapies (section 7.1).

5.3 Benefit-risk assessment

There are sufficient data to support an assessment of benefit and risk for the treatment of NB with CNS/LM metastases with ^{131}I -omburtamab. [REDACTED]

[REDACTED]

5.3.1 Trial objectives

5.3.2 Primary objective

1. To evaluate the overall survival (OS) rate at 3 years.

5.3.3 Secondary objectives

1. To evaluate CNS/LM progression-free survival (CNS/LM PFS) at 6 & 12 months
2. To evaluate Overall Survival (OS) at 12 months
3. To evaluate the objective response rate (ORR) at 6 months.
4. To evaluate dosimetry of ^{131}I -omburtamab.
5. To evaluate the pharmacokinetics of ^{131}I -omburtamab.
6. To evaluate safety of ^{131}I -omburtamab.
7. To evaluate the immunogenicity of ^{131}I -omburtamab.

6 DESCRIPTION OF DESIGN AND TRIAL POPULATION

6.1 Overall trial design and plan

This single-arm, open-label, non-randomized trial includes a screening period followed by treatment and observation periods. At least 32 patients are expected to be enrolled. Before entering the screening period, patients are recommended to have received salvage therapy including surgery, irradiation (preferable craniospinal) and high dose chemotherapy (recommended modalities listed in Appendix 2).

Patients without an objective disease progression (as determined by radiographic examination) 4 weeks after the first infusion and without clinically significant Grade 4 toxicity, are eligible for a second dosing cycle. ^{131}I -omburtamab will be administered via an indwelling intracerebroventricular access device (e.g. Ommaya). In order to avoid an additional procedure and burden to the patient, it can be considered to place the intracerebroventricular access device in connection with the recommended tumor resection procedure (see section 13.4).

After ^{131}I -omburtamab treatment, safety and efficacy will be assessed as described in the flow charts in Table 1 Schedule of time and events with follow-up at week 26 followed by long-term follow up for up to 3 years with regards to survival. An interim analysis, evaluating the dosimetry and pharmacokinetic endpoints as well as available safety and efficacy data, has been conducted on data from patients having received at least treatment cycle 1 (both dosimetry and treatment dose) prior to January 1st, 2020. Starting January 1st, 2020, no further patients will be administered dosimetry doses. After completion of the interim analysis, the dosimetry doses have been removed from treatment cycles. After this, a treatment cycle will take 4 weeks, compared to the previous 5 weeks cycle and will include a treatment dose only followed by an observation period and post-treatment evaluations.

6.1.1 Screening

Screening evaluations (including medical history, physical and neurologic examination, hematology, clinical chemistry) must be completed within 30 days before the first ^{131}I -omburtamab dose at week 1. In case the indwelling intracerebroventricular access device (e.g. Ommaya) is placed in connection with the tumor resection, the informed consent must be obtained prior to the surgery, and before the start of the screening period MRI, CSF cytology and baseline performance testing are to be completed within 3 weeks before the first ^{131}I -omburtamab dose. Adequate CSF flow for ^{131}I -omburtamab intrathecal therapy is determined by Ommaya patency/CSF flow study as outlined in Appendix 4. Patients with obstructive or symptomatic communicating hydrocephalus will be excluded.

6.1.2 Treatment

Patients can be treated in an outpatient setting or may be admitted as inpatients for the treatment infusions. Local safety instructions for storage and handling of radioactive drug products must be strictly followed. Radiation safety precautions may include patient isolation and the use of lead shielding, or designated rooms to ensure that the dose rate in the surrounding areas meets regulatory requirements.

Thyroid protection must be ensured by adequate stable iodide saturation by use of e.g. oral potassium iodide and Cytomel (liothyronine sodium or equivalent). Thyroid protection should be initiated 1 week prior to first ^{131}I -omburtamab infusion in a cycle and continue until 2 weeks after last ^{131}I -omburtamab infusion in the same cycle. Thyroid protection is administered in relation to each treatment cycle. Please refer to section 7.2.5 for details.

[REDACTED]

[REDACTED]

[REDACTED]

[REDACTED]

[REDACTED]

A treatment dose of ^{131}I -omburtamab is administered during week 1. The treatment dose is followed by a 3-week observation period followed by MRI, CSF cytology, and safety monitoring.

6.1.3 Safety considerations

Patients will be monitored for AEs following signing of the informed consent form (ICF).

National Cancer Institute clinical neurotoxicity criteria will be used. All neurologic abnormalities (regardless CTCAE grade) present prior to intrathecal ^{131}I -omburtamab infusions will be recorded as Medical History. In the absence of clear evidence of tumor progression, it may be assumed that new neurological signs and symptoms are treatment related.

Neurotoxicity will also be assessed clinically and radiographically. Assessment of cranial nerves, gross motor function and sensory function will be performed by physical examination. Assessment and grading of radiographically cortical atrophy, cerebral ventricular size, white matter changes or other abnormalities will be made by a neuro-radiologist. Altered CSF flow will be interpreted by the trial nuclear medicine physicians.

Lansky (Karnovsky for children ≥ 16 years) performance score will be analyzed to evaluate gross neurologic function and a measure of a patient's overall function.

Expected risks are described in current ^{131}I -omburtamab IB and section 10.7.

Patients and guardians will be informed of the risk of uncommon or unexpected new side effects.

Expected toxicities will be treated at the discretion of the investigator and could include the following:

[figure not shown]
- Urticaria will be treated with antihistamines.

- During administration of ^{131}I -omburtamab, emergency support for anaphylaxis must be readily available, including epinephrine, diphenhydramine, hydrocortisone, and/or dexamethasone at the bedside.
- Patients with myelosuppression may be supported with blood products or granulocyte-colony stimulating factor according to local standard of care. If indicated, patients also may have banked stem cells reinfused. There is to be a minimum of one week between support for myelosuppression as a stated above and IMP administration.

6.1.4 Duration of treatment

A single treatment cycle will last 4 weeks and includes premedication, intracerebroventricular ^{131}I -omburtamab administration [REDACTED], an observation period, and post-treatment evaluations (see Figure 1 One ^{131}I -omburtamab treatment cycle after the interim analysis).

Figure 1 One ^{131}I -omburtamab treatment cycle after the interim analysis

[figure not shown]
Patients without Grade 4 toxicity and without objective disease progression (as determined by neurologic and/or radiographic examination) by MRI at week 4 in cycle 1 will be eligible to receive a second ^{131}I -omburtamab dosing cycle. Patients with Grade 3 toxicity will receive a second dosing cycle at the discretion of the investigator. For patients presenting with ongoing Grade 3 or 4 myelosuppression at week 4, a delay of dosing cycle 2 for up to 8 weeks can be introduced. Dose delay may be enforced at the discretion of the treating physician.

In case of a subsequent relapse in the CNS/LM during the follow-up period, re-treatment to target minimal residual disease can be considered and allowed in case the patient/parents provide written consent to this. In these cases, it is recommended that patients undergo the salvage treatment as specified in Appendix 2 before subsequent administration of ^{131}I -omburtamab. The administration of ^{131}I -omburtamab in these cases must follow the scheme of the treatment cycle as illustrated in Figure 2.

Patients who complete at least one treatment cycle will be evaluable. All patients who complete at least one treatment cycle (one dose of ^{131}I -omburtamab) will form part of the dataset. However, patients who do not continue to the second treatment cycle (for whatever reason) will be registered as “early treatment discontinuation” in the eCRF. Patients receiving both treatment

cycles of ^{131}I -omburtamab will be registered as “completed treatment” in the eCRF. All evaluable patients will first enter a follow-up period through week 26 (Figure 2) and thereafter the long-term follow-up where patients will be evaluated every half year for up to 3 years post- ^{131}I -omburtamab treatment where after the trial is ended.

)

6.1.5 Screening/pretreatment evaluation

Pre-treatment evaluations should be completed within 30 days of start of treatment, unless otherwise specified, with regards to:

- Informed consent by the patient/patient’s legal guardian(s) and assent by the patient as required by local EC/Institutional Review Board (IRB). Informed Consent must be obtained before any trial related procedures. Procedures or tests that are performed as a part of standard clinical care prior to informed consent, and therefore, not for the purpose of the trial do not need to be repeated at screening if they have been performed within the allowed screening timelines. In these cases, source documents must show that these procedures or tests were performed as standard clinical practice and not for the purpose of the present trial. In case the indwelling intracerebroventricular access device (e.g. Ommaya) is placed in connection with the tumor resection, the informed consent must be obtained prior to the surgery and can be done before the start of the screening period if necessary and up to three months before the start of the screening period.
- Eligibility assessment
- Collection of patient demographic information
- Collection of disease history, including initial diagnosis, dates of initial diagnosis and recurrence, date of CNS/LM metastases diagnosis, prior treatments, and prior surgical interventions as well as outcome of such treatments/ interventions
- Physical examination (including height and weight)
- Vital signs
- Neurologic examination
- Performance testing

- Concomitant medications
 - Complete medical and surgical history
 - Hematology including complete blood count (CBC) with differential count (including eosinophils) and platelet count
 - Clinical chemistry including serum electrolytes (K^+ , Na^+ , Cl^-), creatinine, blood urea nitrogen (BUN), AST, ALT, lactate dehydrogenase (LDH), total bilirubin, albumin, total protein, glucose, T4 and TSH
 - CSF cytology, total protein, glucose cell count
 - Baseline MRI of the brain and spine
 - Placement of an indwelling intracerebroventricular access device (i.e. if not already in place)
 - Ommaya patency/CSF flow study prior to the first infusion
 - Pregnancy testing (only fertile women, experienced menarche prior to screening or during treatment, until week 8)

6.2 Data Monitoring Committee and Adjudication Committee

The data monitoring committee (DMC) is an external committee composed of members whose expertise covers relevant specialties including statistics. The DMC is established to review and evaluate accumulated data from the trial both ad hoc and when 25, 50 and 100% of patients have been enrolled with a maximum interval between meetings of 3 months. The DMC is established to assure patient safety and to evaluate benefit-risk balance during conduct of the trial. The DMC will provide recommendations on trial continuation, modification or termination.

Responsibilities, procedures and workflow of the DMC are specified in the DMC charter.

[REDACTED] We keep the IB as source document for reference safety information and refer to this in the protocol. In addition to listing expected side-effects in protocol section 10.7, to further ensure patient safety, we have included AEs of special interest in protocol section 10.4.

Based on above, no stopping rule is introduced; however, single patient withdrawal criteria's are described in protocol section 6.9.3 in order to ensure patient safety.

Any significant finding/ significant recommendation from the DMC and endorsed by the Sponsors Safety Committee will be communicated to the regulatory authorities.

6.3 Follow-up

Short-term (26 weeks): will include SAE's considered related to ^{131}I -omburtamab or new onset of cancers regardless of causality, physical examinations, concomitant medications, neurological and performance test results and MRI of the brain and spine as described in details in flow charts

in Table 1 **Schedule of time and events**. Pregnancy testing at week 4 and 8 and 26 (only fertile women who have experienced menarche prior to screening or during treatment, until week 8.

Long term (3 years): clinical sites will provide status reports for each patient at 6-month intervals. Details of data collection procedures can be found in the trial flow chart (Table 1 **Schedule of time and events**).

For patients who have relocated back to their home country after the treatment period, the data that would normally be collected at the follow-up visits at the trial hospital can be collected at the referral hospital. The referral hospital is not an investigational site and will not be trained in the protocol. The trial investigator must coordinate the collection of the requested follow-up data every 6 months for up to 3 years following treatment. The safety, survival and relapse status including MRI assessments must be collected to be able to comply with the obligations while ensuring the best possible treatment and safety for the patient. In case the referral site evaluates MRI as to signify CNS/LM progression, this will supersede any other assessment. Ideally the referring oncologist should share the imaging report with the investigator but at the least, the investigator will add notes from the communication with the referring oncologist in the patient files, and the monitor will check consistency between eCRF entry and investigators notes in the patient files (see appendix 6).

6.4 Discussion of trial design

Available clinical data from a single-site trial indicates that treatment with ^{131}I -omburtamab may provide a robust and durable improvement in median survival of NB patients with CNS metastases from 6 to 47 months, providing a reasonable basis for undertaking the present trial when compared to survival for external controls receiving existing therapies. Consequently, an open, single-arm design has been chosen since any controlled design would be considered unethical.

6.5 Selection of trial population

Iodine-131 omburtamab is primarily developed for treatment of NB patients with CNS/LM metastases, a population whose median survival does not exceed 6 months with current treatment options. Patients need to have progressed through induction therapy or have relapsed in CNS/LM following induction.

6.6 Recruitment period

At least 12 months of recruitment time is estimated to be needed to enroll the planned number of patients.

6.7 End of trial

End of trial (EOT) will occur when all patients have been followed until the visit at 3 years, or death whichever comes first.

6.8 Number of participants

At least 32 and a maximum of 50 patients will be enrolled in this trial. With an estimated screen failure rate of 25% it is likely that 40-50 patients will be screened to reach 32 eligible. The patients will be recruited according to institutional guidelines.

6.9 Participant selection and withdrawal

Eligibility will require that the patient meet all inclusion criteria and is not violating any exclusion criterion.

6.9.1 Inclusion criteria

1. Patients must have a histologically confirmed diagnosis of NB with relapse in the CNS or LM.
2. Patients need to have progressed in CNS/LM through induction therapy or have relapsed in CNS/LM following induction. CNS/LM progression/ relapse is defined as LM disease or metastatic deposits in the CNS parenchyma, (excluding skull bone-based metastases).
3. Stable systemic disease not requiring chemo/ immunotherapy as judged by the investigator.
4. VP shunt (only shunts with programmable valves can be accepted) is allowed however should be closed (or adjusted to highest pressure setting) during IMP infusion. It is recommended that the VP shunt remains closed for approximately 5 hours after treatment and then readjusted. The shunt readjustment times are at the discretion of the treating physician. Closure of VP shunt is done at the discretion of the treating physician and the VP shunt should at any time based on patient safety evaluation be re-opened- at the assessment of the treating physician. Patients with ventriculo-atrial or ventriculo-pleural shunts are not eligible.
5. Patients must be between the ages of birth and 18 years at the time of screening.
6. Patients must have a life expectancy of at least 3 months as judged by the investigator.
7. Acceptable hematological status, defined as:
 - Hemoglobin ≥ 8 g/dL
 - WBC count $\geq 1000/\mu\text{L}$
 - Absolute neutrophil count $\geq 500/\mu\text{L}$
 - Platelet count $\geq 50,000/\mu\text{L}$
8. Acceptable liver function defined as:
 - ALT and/or AST ≤ 5 times UNL
 - Bilirubin $\leq 3 \times \text{UNL}$

In case either AST or ALT $\geq 3 \times \text{ULN}$, bilirubin must be $\leq 2 \text{ UNL}$
9. Acceptable kidney function defined as:
 - eGFR $>60 \text{ mL/min}/1.73 \text{ m}^2$ calculated by the 2009 revised Bedside Schwartz Equation (Appendix 3).

10. Written informed consent from legal guardian(s) and/or child must be obtained in accordance with local regulations. Pediatric patients must provide assent as required by local regulations.

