Patient selection criteria	
Inclusion criteria:
 
1. Patients must have a histologically confirmed diagnosis of NB with relapse in the CNS or LM.2. Patients need to have progressed in CNS/LM through induction therapy or have relapsed in CNS/LM following induction. CNS/LM progression/relapse is defined as LM disease or metastatic deposits in the CNS parenchyma, (excluding skull bone-based metastases).3. Stable systemic disease not requiring chemo/immunotherapy as judged by the investigator.4. Ventriculoperitoneal (VP) shunts (only shunts with programmable valves can be accepted) are allowed however should be closed (or adjusted to highest pressure setting) during Investigational Medicinal Product (IMP) infusion. It is recommended that the VP shunt remains closed for approximately 5 hours after treatment and then re-adjusted. The shunt readjustment times are at the discretion of the treating physician. Closure of VP shunt is done at the discretion of the treating physician and the VP shunt should at any time based on patient safety evaluation be re-opened at the assessment of the treating physician. Patients with ventriculo-atrial or ventriculo-pleural shunts are not eligible.5. Patients must be between birth and 18 years of age at the time of screening.6. Patients must have a life expectancy of at least 3 months as judged by the investigator7. Acceptable hematological status defined as:
• Hemoglobin ≥ 8 g/dL• White blood cell (WBC) count $\geq 1000/\mu\text{L}$• Absolute neutrophil count $\geq 500/\mu\text{L}$• Platelet count $\geq 50,000/\mu\text{L}$8. Acceptable liver function defined as:
• ALT and/or AST ≤ 5 times UNL• Bilirubin $\leq 3 \times$ UNL• In case either AST or ALT $\geq 3 \times$ UNL, bilirubin must be ≤ 2 UNL9. Acceptable kidney function defined as:
• Estimated glomerular filtration rate (eGFR) $>60 \text{ mL/min}/1.73 \text{ m}^2$ calculated by the 2009 revised Bedside Schwartz Equation (Appendix 3)10. Written informed consent from legal guardian(s) and/or child must be obtained in accordance with local regulations. Pediatric patients must provide assent as required by local regulations. 
Exclusion criteria:
 
1. Patients with primary NB in CNS.2. Patients must not have obstructive or symptomatic communicating hydrocephalus.3. Patients must not have worsening of neurologic function, according to the assessment by investigator, within 3 weeks prior to first dose of ^{131}I-omburtamab.4. Patients must not have an uncontrolled life-threatening infection.5. Patients must not have received cranial or spinal irradiation less than 3 weeks prior to first dose of ^{131}I-omburtamab in this trial.6. Patients must not have received systemic chemo/immunotherapy (corticosteroids not included) less than 3 weeks prior to enrollment in this trial.7. Patients must not have received any anti-B7-H3 treatment prior to enrollment in this trial.8. Patients must not have severe major non-hematologic organ toxicity; specifically, any renal, cardiac, hepatic, pulmonary, and gastrointestinal system toxicity must fall below

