3 FLOW CHARTS

Table 1 Schedule of time and events

Dosing/Measurements/Evaluations	Trial Periods						
	Screening	1 ³¹ I-omburtamab Treatment Period ¹				Follow-up ²¹	Long Term Follow-up ²¹
	Day -29 to 0	Week 1 & 5	Week 2 & 6	Week 3 & 7	Week 4 & 8	Week 26	Weeks 52, 78, 104, 130 & 156
Informed consent	X ²						
Eligibility check	X						
Demographics, height, and body weight	X						
Medical, surgical and disease history	X						
Prior/concomitant medications	X	X	X	X	X	X ¹⁹	X ¹⁹
TSH/free and total T4 ³	X	X			X	X	X
Physical examination	X	X	X	X	X		
Vital signs ⁴	X	X	X	X	X		
Clinical chemistry & Hematology	X	X	X	X	X		
Performance test ⁶	X ⁵					X	X
MRI of the brain and spine ⁷	X ⁵				X	X ²²	
Neurotoxicity ⁸	X	X			X	X	
Placement of an indwelling intracerebroventricular access device (e.g. Ommaya) ⁹	X						
Ommaya patency/CSF flow study	X						
CSF for cytology, total protein, glucose, and cell count ¹⁰	X ⁵				X	X	
Blocking of thyroid ¹³¹ I uptake ¹¹	X ¹²	X	X		(X) ¹³		
Premedication (oral dexamethasone or an i.v. equivalent) ¹⁴		X					
Premedication with an anti-pyretic ¹⁵		X					
Conditional blood and CSF for culture ¹⁶		X ¹⁶					
Intracerebroventricular ¹³¹ I-omburtamab treatment dose ¹⁷		X					
Adverse events ¹⁸	X	X	X	X	X	X	X

Dosing/Measurements/Evaluations	Trial Periods						
	Screening	¹³¹ I-omburtamab Treatment Period ¹					Follow-up ²¹
		Day -29 to 0	Week 1 & 5	Week 2 & 6	Week 3 & 7	Week 4 & 8	
Pregnancy testing	X ²⁰					X ²⁰	X ²⁰
Clinical response assessment for CNS/LM metastasis ²³	X					X	X
Collection of information on systemic disease progression ²⁴		X	X	X	X	X	X
Collection of information on CNS/LM disease progression ²⁵							X
ADA blood and CSF ²⁶	X					X	
PK blood and CSF ²⁷		X	X				

¹ The ¹³¹I-omburtamab treatment periods is divided in 4-week cycles (if a patient will receive 1 or 2 cycles is at the discretion of the investigator). A cycle consists of a treatment dose in the first week, followed by observation, and samples are taken during week 2 and 3 where after post-treatment evaluations will take place during week 4. For more details about the ¹³¹I-omburtamab cycles see section 6.1.4.

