² Informed Consent must be obtained before any trial related procedures. Procedures or tests that are performed as a part of standard clinical care prior to informed consent, and therefore, not for the purpose of the trial, do not need to be repeated at screening if they have been performed within the allowed screening timelines. In these cases, source documents must show that these procedures or tests were performed as standard clinical practice and not for the purpose of the present trial. In case the indwelling intracerebroventricular access device (e.g. Ommaya) is placed in connection with the tumor resection, the informed consent must be obtained prior to the surgery and can be done before the start of the screening period if necessary. The investigator is responsible for documenting this properly.

³ Thyroid stimulating hormone (TSH)/ free and total T4 to be assessed at screening, pre-dose week 1 and 4, pre-dose week 5 and 8, week 26 if applicable and weeks 52, 78, 104 130 and 156.

⁴ Measurements of pulse oximetry, heart rate, respiratory rate, temperature, and blood pressure.

⁵ To be performed within 3 weeks prior first IMP infusion.

⁶ Lansky Scale < 16 years, Karnofsky Scale \geq 16 years. Post week 26 every 6 months.

⁷ (Magnetic resonance imaging of the brain and spine to be completed before first IMP administration), at week 4 (\pm 4 days), 8 (\pm 4 days) and 26 (\pm 24-29 weeks)

⁸ Gross investigation of cranial nerves by physical examination and radiographical investigation as described in section 6.1.3. Evaluating neurological Adverse Events (AEs), the National Cancer Institute clinical neurotoxicity criteria will be used. Any patient that develops a Grade 4 neurotoxicity must be discontinued from treatment. The clinical neurotoxicity evaluation is to be conducted at screening and weeks 1, 4, 5, 8 and 26. The radiographic assessment of neurotoxicity and disease progression (by MRI) is to be conducted at screening, weeks 4 and 8 and week 26.

⁹ Only for patients who do not have an intracerebroventricular device already placed. The procedure must be conducted prior to first dose and after the patient has been assessed to be eligible to enter the trial.

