7.1.1 Treatment

One ^{131}I -omburtamab cycle takes 4 weeks and includes a treatment dose followed by an observation period and post-treatment evaluations. The treatment dose is administered on day 1 of the first week in a cycle (according to **Table 1**). The patient will be followed for 4 weeks after the treatment dose. A full treatment is achieved when both cycles have been completed. Patients who finish both treatment cycles and complete week-8 assessments will enter the short-term follow up phase. Patients who finish only one treatment cycle will be registered as early treatment discontinuation and continue to the short-term follow-up visit at week 26. Please see Duration of treatment section 6.1.4.

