9.1.2.7 ***Anti-Drug-Antibody effects on PK and Safety.***

The ADA characterization will deliver occurrence rate of neutralizing antibodies in blood and cerebrospinal fluid (CSF) of exposed patients. Potential associated effects of any neutralizing ADA's on ^{131}I -omburtamab pharmacokinetics (PK) in blood and CSF and safety will be investigated.

9.1.2.7.1 *ADA effects on PK*

Radioactivity counts in blood and CSF will be measured at the following time points after treatment with ^{131}I -omburtamab:

- 1h after treatment
- 6h after treatment
- 24 after treatment
- 7 days after treatment.

The analysis will comprise an intra-patient comparison of PK parameters from the two dose administrations in patients with and without presence of neutralizing ADAs in blood or CSF.

9.1.2.7.2 *ADA effects on Safety*

The analysis will comprise a comparison of reported safety events after the second dose administration in patients with and without presence of neutralizing ADAs in blood or CSF.

9.2 **Other assessments**

9.2.1 **Hematology and clinical chemistry**

Hematology and clinical chemistry will be measured by a local laboratory during screening and in all following treatment cycles and will assess liver and kidney function (ALT, AST, alkaline phosphatase, albumin, bilirubin, BUN, glucose and creatinine), total protein and serum electrolytes (sodium, potassium, chloride and bicarbonate). Complete differential blood count, including eosinophils and platelets, will be performed during screening and in the cycles up to the follow-up at week 26. Thyroid stimulating hormone (TSH)/ free and total T4 to be assessed at screening, pre-dose week 1 and 4, pre-dose week 5 and 8, week 26 if applicable and weeks 52, 78, 104 130 and 156..

If abnormal serum glucose (CTCAE \geq Grade 2) is obtained, a fasting serum glucose is to be obtained at next patient visit. AE reporting of hyperglycemia will require fasting values to assess CTCAE grading.

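### The blood-count thresholds of inclusion criterion 7 can be met on a count up to 30 days old at the first infusion, and no readable text ties the week-1 count to dose 1

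*Combined protocol and SAP*

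**What the plan says.** - **Thresholds.** Criterion 7 in 6.9.1 ("Acceptable hematological status, defined as") and in the synopsis ("Acceptable hematological status defined as") requires hemoglobin of at least 8 g/dL, white cells of at least 1000/µL, neutrophils of at least 500/µL and platelets of at least 50,000/µL. Neither place gives a date for the sample.
- **Window.** Section 6.1.1 places screening hematology in the general window: "hematology, clinical chemistry) must be completed within 30 days before the first" dose. Section 6.1.5, whose list includes the blood count, says "Pre-treatment evaluations should be completed within 30 days of start of treatment, unless otherwise specified". Table 1 shows screening as Day -29 to 0 and marks the eligibility check in that column only.
- **Reuse.** Under footnote 2 of Table 1, routine-care tests "do not need to be repeated at screening if they have been performed within the allowed screening timelines". Section 6.1.5 repeats this.
- **Week 1.** The Table 1 row "Clinical chemistry & Hematology" is marked at screening and again in weeks 1 and 5, 2 and 6, 3 and 7, and 4 and 8. Section 9.2.1 says of the differential count that it "will be performed during screening and in the cycles up to the follow-up at week 26". Neither place says whether the week-1 sample comes before or after the dose.
- **Dose.** Section 7.1.1: "The treatment dose is administered on day 1 of the first week in a cycle".

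**The concern.** Thresholds of this kind are meant to protect the child at the time of infusion. Section 10.7 names neutropenia, and myelosuppression needing red-cell or platelet transfusion, among the risks of the product. Section 13.4 acknowledges that high-dose chemotherapy before screening may itself suppress the marrow, and Appendix 2 lists stem cell rescue if needed. Counts may therefore be moving during the screening window.

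A child who met criterion 7 early in that window could have fallen below it by dose 1. On the readable text, dosing that child would still comply with the protocol. A week-1 count drawn after the infusion would comply as well.

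**Working it through.** **1. Reproduce the window.** Screening opens on Day -29 (Table 1) and the dose is on Day 1 (7.1.1). Oldest permitted count: 1 - (-29) = 30 days. This agrees with the 30 days in the synopsis, 6.1.1 and 6.1.5.

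**2. Look for a shorter limit.** Section 6.1.5 yields to anything more specific. Footnote 5 gives a three-week limit, but attaches it to the performance test, MRI and CSF rows, not to hematology. Exclusion criteria 3 and 5 are counted back from the first dose; criterion 7 is not. The 30 days stand.

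**3. Compare how week-1 assessments are timed.**

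| Assessment | Scheduled in week 1 | Stated to be before the dose |
|---|---|---|
| TSH/T4 | Yes | Yes (footnote 3; 9.2.1) |
| Vital signs | Yes | Yes, with a second reading 30 minutes after (9.2.9) |
| Hematology | Yes | No |

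**4. Look for a rule under which a low count holds dose 1.**

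- 7.1 requires screening assessments to be evaluated before treatment and all criteria to be met. 7.2.1 makes the investigator responsible for dosing only eligible patients. Neither dates the count, so one that is 30 days old satisfies both.
- 6.1.3 and 7.3.1 require a week between hematological support and dosing. This restricts support and sets no count.
- 6.1.4 allows cycle 2 to be delayed for ongoing Grade 3 or 4 myelosuppression at week 4. It is optional and does not cover dose 1. The treating physician may also delay a dose, but no threshold is attached.
- 6.9.3 lists no blood-count threshold among the discontinuation criteria.
- 11.1 requires Grade 4 laboratory values to be retested within 24 hours of the result. That is an action on counts, but not a condition for dosing.

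**5. Illustrate what the age of the count can mean.** Assume that week -5 of Appendix 2 starts 5 × 7 = 35 days before dose 1 and that the whole chemotherapy block is given over five consecutive days, 35 to 31 days before the dose. The last chemotherapy is then L = 31 days before dose 1. Days from last chemotherapy to the count = L - age of the count.

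| Timing of dose 1 (assumed) | L | Count 30 days old | 14 days old | 7 days old |
|---|---|---|---|---|
| As in Appendix 2 | 31 | 1 | 17 | 24 |
| One week later | 38 | 8 | 24 | 31 |
| Two weeks later | 45 | 15 | 31 | 38 |

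Exclusion criterion 6 does not rule out the 1-day cell. It counts three weeks back from enrollment, so with L = 31 enrollment must fall no more than 31 - 21 = 10 days before the dose. A count that is 30 days old at the dose is then at least 30 - 10 = 20 days old at enrollment, which the criterion does not forbid.

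The enrollment date is not defined. If it coincided with the dosing day (assumption), chemotherapy could end 21 days before dose 1, and a qualifying count could precede its end by 30 - 21 = 9 days. That would depart from the recommendation in 6.1 that salvage therapy come before screening.

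**The case against.** The strongest objection is that the absence of a check cannot be confirmed. Several blocks of 6.1.2 are redacted just before the sentence on the week-1 dose, and 6.1.4 has a redaction at the administration step. Footnotes 14 and 15 show that 6.1.2 covers premedication, but not that premedication fills every block. This stands: the point can be made only about readable text, and the fix has to allow for an existing rule.

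It also stands that the protocol already provides much of what is needed. A week-1 count is scheduled, a pre-dose week-1 blood sample is already required for TSH/T4, and Grade 4 values are retested. Anti-cancer therapy is barred from week -3, support is barred in the week before dosing, and the physician may delay. A reader might infer that no blood count is called for around dose 1. The documents do not support that. What is missing is the order of sample and dose, and a consequence if the result is low.

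A reader might also take the 1-day figure as typical, or infer that children will be infused while below the thresholds. Neither follows. The figure needs the oldest permitted count, assumed chemotherapy dates and later results being ignored. Appendix 2 is a recommendation subject to the treating physician's judgment. Where stem cell rescue is used, a count one day after chemotherapy may also precede the end of salvage therapy. The documents give no time course for the counts.

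One part does not stand: that the duty to treat only eligible patients closes the gap. Under 7.2.1 the product is prepared once a patient has been found eligible, so eligibility is settled before the dose is made and need not rest on a day-1 sample.

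**Conclusion.** The point holds in limited form. Criterion 7 can be met on a count up to 30 days old at the first infusion. The week-1 count is not labelled pre-dose, and no readable passage makes dose 1 depend on it. The 30 days rest on the protocol's own dates and need no assumption.

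The clinical size of the gap is unknown. The number of children below a threshold at dose 1 cannot be derived, and the intervals after chemotherapy are illustrations under assumed timing. The change is worth making because it ties a test already scheduled to thresholds already set. Confidence is moderate, because redacted text in 6.1.2 or 6.1.4 may already contain the rule.

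**What to change.** 1. In Table 1 and 9.2.1, label week-1 hematology as pre-dose. It can be drawn with the pre-dose TSH/T4 sample.
2. In 6.9.1 and the synopsis, require the criterion 7 thresholds to be met on the most recent count, taken within a short interval before the first infusion, and hold dose 1 otherwise. The sponsor should set the interval. Seven days is only an example, and nothing in the documents supports that figure in particular.
3. In footnote 2 and 6.1.5, limit the reuse of routine-care counts to the same interval.
4. If a redacted passage already contains this check, refer to it from criterion 7 instead.

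The thresholds do not change. The cost is a few sentences and one table label. Some first doses will be postponed. Because the product is made on demand, a dosing-day result could arrive after the dose has been prepared, so one draw may have to be moved or added a few days earlier, ideally before the dose is ordered.
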